2.2 Study Schematic

Figure 1: Study Design

ApoE ε4 +/- = apolipoprotein E4 positive/negative; FU = follow-up; P = placebo; R = randomization date.

CONFIDENTIAL

^{*}Subjects who are assigned to placebo during the placebo-controlled period are randomized in a 1:1 ratio to high and low dose aducanumab treatment (stratified by their ApoE \(\xi \)4 carrier status) for the long-term extension period on Study Day 1.

Final V1.0

2.3 Schedule of Events for LTE period

See protocol section 4.2.

3 STATISTICAL ANALYSIS METHODS

3.1 General Considerations

This statistical analysis plan (SAP) covers the analyses of the LTE period and the analyses across both the placebo-controlled period and the LTE period.

Summary tables will be presented using descriptive summary statistics. For continuous variables, summary statistics will generally include: number of subjects with data, mean, standard deviation, median, 25% percentile, 75% percentile, minimum and maximum. For categorical variables, this will generally include: number of subjects randomized or dosed, number with data, and the percent of those with data in each category.

There are two types of analysis displays for the analyses of the LTE period: by LTE treatment group (analysis display A in Appendix 4.1) and by LTE treatment group stratified by ApoE status (analysis display B in Appendix 4.1; here ApoE status refers to the status recorded in IXRS [see Table 2 for correspondence between LTE treatment groups and LTE treatment groups stratified by ApoE status]). The analysis display for each analysis will be defined in each section. All the listings will be presented by LTE treatment group stratified by ApoE status, unless otherwise specified.

Unless otherwise specified, baseline refers to the baseline value for the placebo-controlled period and is defined as the most recent non-missing measurement collected prior to the first dose. Change from baseline will be defined as post-baseline value minus baseline value.

Unless stated otherwise, all statistical tests will be 2-sided with statistical significance level of 0.05.

The statistical software, SAS® will be used for all summaries and analyses.

3.1.1 Analysis Population

- Intent-to-treat (ITT) population: The Intent-to-treat population is defined as all randomized subjects who received at least one dose of study treatment (aducanumab or placebo).
- ¹⁸F-florbetapir amyloid PET analysis population:
 The ¹⁸F-florbetapir amyloid PET analysis population is defined as all randomized subjects who received at least one dose of study treatment (aducanumab or placebo), used ¹⁸F-florbetapir ligand for amyloid PET scan, and had an evaluable baseline amyloid PET SUVR value for the composite region-of-interest using cerebellum as the reference region.
- ¹⁸F-flutemetamol amyloid PET analysis population:

Final V1.0

The ¹⁸F-flutemetamol amyloid PET analysis population is defined as all randomized subjects who received at least one dose of study treatment (aducanumab or placebo), used ¹⁸F-flutemetamol ligand for amyloid PET scan, and had an evaluable baseline amyloid PET SUVR value for the composite region-of-interest using cerebellum as the reference region.

• Safety population:

The safety population is defined as all randomized subjects who received at least one dose of study treatment (aducanumab or placebo). It is the same population as the ITT population.

• Safety MRI population:

The safety MRI population is defined as all randomized subjects who received at least one dose of study treatment (aducanumab or placebo) and had at least one post-baseline MRI assessment.

• PK analysis population:

The PK analysis population is defined as all randomized subjects who received at least one dose of study treatment (aducanumab or placebo) and had at least one measurable aducanumab concentration in serum.

• Immunogenicity population:

The analysis population for immunogenicity is defined as all randomized subjects who received at least one dose of study treatment (aducanumab or placebo) and had at least one post-dose sample evaluated for immunogenicity.

3.1.2 Analyses period

Depending on the purpose, different analyses will be conducted on the following study periods:

- 1. LTE period. Only data in the LTE period will be included in these analyses. For example, incidence table of adverse events in the LTE period.
- 2. Placebo-controlled and LTE period. All the data in the placebo-controlled and LTE periods will be included in these analyses. For example, mean plot of actual laboratory values in the placebo-controlled and LTE period.
- 3. Placebo-controlled and LTE active treatment period. Active treatment period is defined as the study period(s) that a subject is assigned to aducanumab. For early start subjects subjects who are assigned to aducanumab in both placebo-controlled and LTE period, all the data (placebo-controlled and LTE periods) will be included in the analyses. For late start subjects subjects who are assigned to aducanumab in the LTE period, only data in the LTE period will be included. For example, incidence table of adverse events in the placebo-controlled and LTE active treatment period.

Final V1.0

Subjects to be included in a certain output is determined by both the analysis population and the analysis period. For example, the incidence table of adverse events in the LTE period will include subjects in the safety population for the LTE period, i.e., all randomized subjects who received at least one dose of study treatment in the LTE period. The incidence table of adverse events in the placebo-controlled and LTE active treatment period will include subjects in the safety population for the active treatment period, i.e., all randomized subjects who received at least one dose of study treatment in the active treatment period. In this SAP we do not separately define the analysis population in each analysis period.

3.2 Background Characteristics

The summaries in this section will be based on the ITT population. Analysis period will be specified for each table or figure. Unless otherwise specified, summary tables will be presented by LTE treatment group and by LTE treatment group stratified by ApoE status (see Table 2 for correspondence between LTE treatment groups and LTE treatment groups stratified by ApoE status). Listings will include all data in the placebo-controlled and LTE periods (all data in the study), with an indicator of the study period (pre-dosing, placebo-controlled, or LTE) for each record to indicate when the event occurred. Listings will be presented by LTE treatment group stratified by ApoE status.

3.2.1 Accounting of Subject

Disposition in the LTE period will be summarized for subjects enrolled in LTE. The summary data will include number (%) of subjects dosed in the LTE period, number (%) of subjects who completed the treatment/study in LTE, and number (%) of subjects who discontinued treatment and/or withdrew from study in LTE. For subjects who discontinued treatment and/or withdrew from study, the reasons for discontinuation and/or withdrawal, days on treatment and days on study will be summarized and listed. Time to treatment discontinuation and time to study withdrawal in the LTE period will be displayed by Kaplan-Meier plot (presented by LTE treatment group).

3.2.2 Demographics and Baseline Characteristics

Demographics, baseline characteristics, medical history and AD treatment history will be summarized for subjects enrolled in the LTE period and subjects not enrolled in the LTE period, respectively. Demographics and baseline characteristics will also be summarized for all ITT subjects (presented by LTE treatment group). Please refer to the SAP for the placebocontrolled period for more details.

3.2.3 Concomitant Medications and Non-Drug Therapies

The number (%) of subjects taking concomitant medication and non-drug therapies in the LTE period will be summarized. Non-drug therapies will be presented by LTE treatment group. In addition, number of subjects in the ITT population that have taken any concomitant medications in the placebo-controlled and LTE active treatment period will be summarized. Concomitant medications and non-drug therapies will be listed.

Final V1.0

For subjects enrolled in the LTE period, the number (%) of subjects taking concomitant AD symptomatic medications, number of subjects using Cholinesterase inhibitors only, Memantine only, or both at the baseline of the placebo-controlled period will be summarized. A similar summary will be provided for subjects taking AD symptomatic medication concomitantly at the baseline of the LTE period. Subjects who have any change in AD symptomatic medications during the LTE period will be summarized by the timing of change, i.e., the number of subjects changing between Week 80 and Week 106, the number of subjects changing between Week 134, etc. The summary for AD symptomatic medication use during the LTE period will be presented by LTE treatment group. The start and stop date of AD symptomatic medication will be listed for subjects who have any change to AD symptomatic medications during the combined placebo-controlled and LTE periods. Please refer to the placebo-controlled SAP for definitions of concomitant therapies and AD symptomatic medication use at baseline.

3.2.4 Protocol Deviations

Protocol deviations identified during site monitoring will be captured in a Protocol Deviation log and categorized as major or minor deviations based on Protocol Deviation Classification (see Appendix of the placebo-controlled SAP). The major protocol deviations occurred in the LTE period will be summarized for subjects enrolled in LTE. The major protocol deviations for all ITT subjects in the combined placebo-controlled and LTE periods will also be summarized. Major and minor protocol deviations for all ITT subjects will be listed, respectively, across the placebo-controlled period and the LTE period. All summaries for protocol deviations will be presented by LTE treatment group.

3.2.5 Study Drug Exposure and Study Drug Compliance

A summary table of study drug exposure and compliance in the LTE period will be provided. Number of infusions (aducanumab or placebo) received will be summarized as a categorical variable (categories of 1-5, 6-10, 11-15, 16-20, 21-26, 27-39, 40-52 and 53-65) as well as a continuous variable. Number of weeks on study treatment (aducanumab or placebo), calculated as (date of last dose – date of first dose +29)/7, will be summarized as a categorical variable (every 6 months for the first 2 years of LTE, and then every year) as well as a continuous variable. Percentage of study treatment taken up to the last dose, calculated as (the actual number of infusions / by the number of infusions a subject is expected to take until the date of last infusion)*100, will be summarized as a continuous variable. This table will be presented by LTE treatment group. A similar table will also be provided on the placebocontrolled and LTE active treatment period in order to summarize the exposure data while subjects are on aducanumab.

Due to the use of titration regimen in the study and possible dose reduction due to ARIA, another summary table will be provided including the following information in the LTE period: number of total infusions (categories of 1-5, 6-10, 11-15, 16-20, 21-26, 27-39, 40-52 and 53-65) as well as a continuous variable, number of infusions at each dose level (1 mg/kg, 3 mg/kg, 6 mg/kg and 10 mg/kg, respectively) summarized as a categorical variable as well as a continuous variable, number of subjects with dose increase (placebo to 1 mg/kg, 1 to 3 mg/kg, 3 to 6 mg/kg and 6 to 10 mg/kg, respectively), number of subjects with dose reduction (1 mg/kg to placebo, 3 to 1 mg/kg, 6 to 3 mg/kg and 10 to 6 mg/kg, respectively), maximum

Final V1.0

dose level received, and cumulative dose (as a continuous variable). This table will be summarized by LTE treatment group stratified by ApoE status. A similar table will also be provided on the placebo-controlled and LTE active treatment period in order to summarize the titration and dose reduction data while subjects are on aducanumab.

A listing of study drug administration records, including dose level at each infusion, cumulative number of infusions and cumulative dose will be provided for the placebocontrolled and LTE period. A listing of aducanumab lot numbers will be provided for the placebo-controlled and LTE period.

3.3 Efficacy Analysis

3.3.1 General Considerations

The analysis population for efficacy analysis is the same as the ITT population and data from both the placebo-controlled and LTE periods will be included. All efficacy analyses will be presented by LTE treatment group, i.e, late start low dose, late start high dose, early start low dose, early start high dose (analysis display A in Appendix 4.1).

The following two comparisons will be evaluated for the long-term efficacy of aducanumab:

- The early start low dose compared with the late start low dose;
- The early start high dose compared with the late start high dose.

There will be no multiple comparison adjustments.

Visit windows for mapping efficacy endpoint

For efficacy data that are summarized or analyzed by visit, data collected on all scheduled visits and all unscheduled visits will be mapped to an appropriate analysis visit using the windowing scheme shown in Table 3. If there are 2 or more assessments available in the same analysis window for a subject, the assessment that is closest to the target visit day will be used for analysis. If there are 2 or more assessments in the same analysis window with the same distance from the target visit day, the later assessment will be used.

Table 3: Visit Windows for Efficacy Endpoints

Analysis visit	Target visit day	Analysis visit window
Baseline	1	Most recent non-missing pre-dose value
Week 26	183	[92, 266]
Week 50	351	[267, 448]
Week 78	547	[449, the end day of the placebo-controlled period*]
Week 106	743	[645, 840]
Week 134	939	[841, 1036]
Week 162	1135	[1037, 1204]

CONFIDENTIAL

Final V1.0

Analysis visit	Target visit day	Analysis visit window	
Week 182	1275	[1205, 1365]	
Week 232	1625	[1535, 1715]	
Week 284	1989	[1899, 2079]	
Week 338	2367	≥ 2277	

^{*} The end day of the placebo-controlled period is the last day before the first infusion in LTE for subjects who enter LTE, and is the last day in study for subjects who do not enter LTE.

Handling of missing items for scales

Please refer to the placebo-controlled SAP for the imputation method. Same method will be applied to efficacy endpoints collected in the LTE period.

3.3.2 By Visit Summary and MMRM Model

The baseline and change from baseline CDR-SB scores at each post-baseline visit will be summarized by LTE treatment group. A mixed model repeated measures (MMRM) model will be used to analyze change from baseline CDR-SB using fixed effects of LTE treatment group, time (categorical), LTE treatment group-by-time interaction, baseline CDR-SB, baseline CDR-SB by time interaction, baseline MMSE, AD symptomatic medication use at baseline (yes/no), region, and laboratory ApoE & status (carrier/non-carrier). An unstructured covariance matrix will be used to model the within-patient variance-covariance errors. If the unstructured covariance structure matrix results in a lack of convergence, the heterogeneous Toeplitz covariance structure followed by the heterogeneous first-order autoregressive covariance structure will be used. The Kenward-Roger approximation will be used to estimate the denominator degrees of freedom. Visits with too few data may be excluded from the MMRM analysis and be analyzed by ANCOVA instead.

The by visit summary and MMRM analysis will be similarly performed for CDR cognitive subscore, CDR functional subscore, MMSE, ADAS-Cog 13, ADCS-ADL-MCI and NPI-10. Only the by visit summary will be performed for CDR box scores and informant-rated EQ-5D. The distribution of CDR global score will be summarized as a categorical variable at each post-baseline visit.

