	High Dose - ApoE ε4 (-)	1	1	3	3	6	6	10
Low Dose	Low Dose - ApoE ε4 (+)	1	1	3	3	3	3	3
	Low Dose - ApoE ε4 (-)	1	1	3	3	3	3	6
Placebo	Placebo - ApoE ε4 (+)	saline						
	Placebo - ApoE ε4 (-)	saline						

¹ 10 mg/kg is the target dose for all ApoE ε4 carriers assigned to the aducanumab high-dose group. Subjects enrolled under protocol versions 1-3 and assigned to the previous high-dose of 6 mg/kg will be titrated to 10 mg/kg upon receipt of at least 2 doses at 6 mg/kg.

At the end of the double-blind, placebo-controlled treatment period, subjects who meet the extension entry criteria may enter a long-term safety and efficacy extension period, with all subjects receiving aducanumab approximately every 4 weeks (up to a total of 65 doses over 5 years). The treatment group for the LTE period will be assigned at the same time as the randomization for the placebo-controlled period, regardless of whether a subject entering the LTE period or not. Subjects who are assigned to the placebo group during the placebo-controlled period will be assigned to 1 of 2 active treatment groups in a 1:1 ratio (aducanumab low dose: aducanumab high dose) and randomization will be stratified by their ApoE ε4 carrier status; for those who enter the LTE period, aducanumab will be titrated for up to 6 doses prior to reaching the target dose following the same schedule described for the placebo-controlled period. Subjects who are assigned to either aducanumab low dose or aducanumab high dose group in the placebo-controlled period will continue in the same treatment group for the LTE period; those who enter the LTE period will maintain the dosing scheme outlined in the protocol at the time of transition from the placebo-controlled period to the LTE period (e.g. subjects who are on stable dosing in the placebo-controlled period will continue on the same dose, subjects who are on a titration regimen during the transition will continue to titrate into the LTE period, and ApoE & carrier subjects who are enrolled in the LTE and randomized to the high-dose group prior to implementation of version 4 of the protocol will be allowed to titrate to 10 mg/kg). Aducanumab will be titrated for up to 6 doses prior to reaching the target dose for the late start subjects as shown in Table 2 and Figure 1.

² ApoE ε4 status recorded in the Interactive Voice/Web Response System (IXRS).

Final V1.0

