For the ¹⁸F-florbetapir amyloid PET analysis population, an MMRM model will be used to analyze change from baseline SUVR for each target ROI with cerebellum as the reference region for all the visits in the placebo-controlled and LTE period. Fixed effects of the model will include LTE treatment groups, visit, treatment group-by-visit interaction, baseline SUVR (continuous), baseline SUVR by visit interaction, baseline MMSE (continuous), laboratory ApoE & status (carrier and non-carrier), and baseline age (continuous). Visit and treatment group will be treated as categorical variables in the model along with their interactions. An unstructured covariance matrix will be used to model the within-patient variance-covariance errors. If the unstructured covariance structure matrix results in a lack of convergence in any of the parameters, the heterogeneous Toeplitz covariance structure followed by the heterogeneous first-order autoregressive covariance structure will be used for all the parameters. The Kenward-Roger approximation will be used to estimate the denominator degrees of freedom. Adjusted means for each treatment group, pairwise adjusted differences for the comparisons, 95% confidence intervals for the differences and associated p-values will be presented at each visit. Visits with too few data may be excluded from the MMRM analysis and be analyzed by ANCOVA instead. The same MMRM model will also be used to analyze the change from baseline SUVR for the composite ROI with each of the reference regions. No multiple comparison adjustment will be used for amyloid PET analysis.

Visit Windows for by visit analyses

Statistical Analysis Plan

Long-Term Extension Period

Final V1.0

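### The LTE repeated-measures models fit two means to one placebo arm at the pre-LTE visits, an avoidable loss of precision (not a bias) in tertiary analyses

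*SAP*

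**What the plan says.** The LTE SAP, 2.1, makes the LTE assignment at the initial randomisation, whether or not the subject later enters the extension. Placebo subjects "will be assigned to 1 of 2 active treatment groups in a 1:1 ratio", low or high dose, stratified by ApoE ε4 carrier status. Table 1 gives all placebo subjects saline for all 20 doses, and 2.1 keeps investigators and subjects blinded to the assignment.

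For LTE efficacy, 3.3.1 states that "data from both the placebo-controlled and LTE periods will be included", and its Table 3 lists Weeks 26, 50 and 78 as analysis visits. The Week 78 window closes on the day before the first LTE infusion. Two comparisons are named: "The early start low dose compared with the late start low dose" and "The early start high dose compared with the late start high dose".

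The model in 3.3.2 is fitted "using fixed effects of LTE treatment group, time (categorical), LTE treatment group-by-time interaction, baseline CDR-SB", plus further covariates. Section 3.4.4 does the same for amyloid PET: "Fixed effects of the model will include LTE treatment groups, visit, treatment group-by-visit interaction", fitted "for all the visits in the placebo-controlled and LTE period". For PET the reporting rule is explicit: "95% confidence intervals for the differences and associated p-values will be presented at each visit".

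Nothing in the LTE SAP pools or constrains the two late-start means before the LTE. Appendix display A has a late-start total column, but no model or contrast uses it.

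**The concern.** Until the first LTE infusion, late-start low and late-start high differ only by a blinded random label. Their expected changes at Weeks 26, 50 and 78 are therefore equal by design, not by a modelling assumption. A full group-by-visit interaction fits six late-start means where the design supports three (four instead of two for PET). Each dose-matched contrast at those visits then rests on about half the placebo arm, and the low and high doses are set against different placebo means.

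The loss also reaches the LTE visits. When pre-LTE means are estimated separately, the model cannot use the known equality to correct a chance imbalance between the halves that carries forward within subjects.

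The two early-versus-late contrasts are the only long-term efficacy comparisons named. The 3.3.2 model is repeated for both CDR subscores, MMSE, ADAS-Cog 13, ADCS-ADL-MCI and NPI-10. Precision that costs no data is worth having there.

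**Working it through.** **Inputs from the documents.** Final size 1605, allocation 1:1:1, so 535 per group. Placebo split 1:1, so 535/2 = 267.5 per late-start group. Planning values in the placebo-controlled SAP, section 3: difference 0.5, SD 1.92, two-sided 0.05, dropout 30%, about 90% power with 450 per group.

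**Assumed, because the documents give no figures.** Within-subject correlations, LTE visit SDs and LTE retention.

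**1. The plan's own figure.** n = 2(1.960 + 1.282)² × 1.92²/0.5² = 310 evaluable per arm; 310/0.70 = 443, close to 450. With 450 × 0.70 = 315 evaluable per arm, power is 90.5%. The planning figure reproduces.

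**2. Pre-LTE visits.** For one early-start group against placebo:
- whole placebo arm: variance proportional to 1/535 + 1/535 = 2/535
- one late-start half: 1/535 + 1/267.5 = 3/535
- ratio 3/2 = 1.5; standard error ratio √1.5 = 1.22

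A generalised least-squares calculation with monotone dropout (assumed retention 90/80/70/55%) gave 1.2247 for the standard error at Weeks 26, 50 and 78 under correlations of 0.5, 0.7 and 0.9. The ratio needs only equal arms, an even split and similar dropout. In the PET subset it holds approximately, since an even split is only expected there.

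**3. On the CDR-SB scale at Week 78.** With 535 × 0.70 = 374.5 evaluable per arm:
- whole arm: SE = 1.92 × √(2/374.5) = 0.140; 95% half-width 0.275; power for 0.5 points 94.6%
- half arm: SE = 1.92 × √(3/374.5) = 0.172; 95% half-width 0.337; power 82.9%

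The power figures only illustrate scale; the LTE SAP sets no power target.

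**4. LTE visits, complete data.** Let ρ be the multiple correlation of an LTE visit with Weeks 26-78, and n = 535.
- Separate pre-LTE means: contrast variance = (σ²/n)(1 + 2) = 3σ²/n.
- Shared pre-LTE mean: the part of the late-start mean predicted from earlier visits is now known from the whole arm, so its variance is (σ²/n)[2(1 − ρ²) + ρ²] = (σ²/n)(2 − ρ²). The contrast variance is (σ²/n)(3 − ρ²).
- Ratio: 1 − ρ²/3.

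Under a first-order autoregression with correlation r per 26 weeks, ρ = r^(28/26) at Week 106 and r^(104/26) = r⁴ at Week 182:

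| r | ρ, Week 106 | variance cut | ρ, Week 182 | variance cut |
|---|---|---|---|---|
| 0.5 | 0.47 | 7% | 0.06 | 0.1% |
| 0.7 | 0.68 | 15% | 0.24 | 2% |
| 0.8 | 0.79 | 21% | 0.41 | 6% |
| 0.9 | 0.89 | 27% | 0.66 | 14% |

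**5. Other assumptions.** Adding random-slope covariances, and assumed retention of 60% at Week 106 and 38% at Week 182, to the r = 0.7-0.9 cases gives cuts of about 13-27% at Week 106 and 1-27% at Week 182. The top of the Week 182 range needs random slopes. At Week 106, 1/0.869 = 1.15 and 1/0.734 = 1.36, so the gain there is worth about 15-36% more subjects. As standard errors, the step 2 calculation puts the separate-means model 1.05, 1.10 and 1.17 times above the shared-mean model at Week 106 for equal correlations of 0.5, 0.7 and 0.9.

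**The case against.** The planned model is a standard one. The split is randomised, so the half-arm contrasts are unbiased and their standard errors correct; a chance difference between the halves is ordinary sampling error, already in the confidence interval. That stands. A reader might infer that the long-term comparisons are biased or invalid, and the documents do not support that.

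A reader might also infer that every early-versus-late comparison wastes half the placebo arm. It does not. From the first LTE infusion the two late-start groups follow different dose schemes (LTE SAP, Table 2), so half an arm per dose-matched contrast is then part of the design. Only the indirect gain through correlation is avoidable at those visits.

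The factor of 1.5 applies to visits already compared with the whole placebo arm in the placebo-controlled SAP (4.3.2.1; 4.4.4 for PET). Only the PET section says that contrasts will be reported at every visit. For the clinical scales, reporting of Week 26-78 contrasts from the LTE model is possible but not stated.

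The gain at LTE visits rests on correlations and retention that the documents do not give, and may be close to nil at Week 182. The endpoints are tertiary and carry no multiplicity adjustment. All of this limits the size of the point. None of it gives a reason to estimate separately two means that randomisation makes equal.

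**Conclusion.** The point holds as a modest, cheaply corrected loss of precision in tertiary analyses. The 1.5-fold variance at the pre-LTE visits follows from the 1:1 split and equal arms and is firm. It applies to any early-versus-late contrast that the LTE models report there, which is certain for PET at Weeks 26 and 78. The loss at LTE visits is real in direction but uncertain in size: about 13-27% of variance at Week 106 for correlations of 0.7-0.9 per 26 weeks, about 7% at 0.5, and about 1-27% at Week 182. The primary analysis and the other placebo-controlled results use the whole placebo arm and do not change.

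**What to change.** In LTE SAP 3.3.2 and 3.4.4, replace the group, visit and interaction terms with one group-by-visit cell factor. In it, late-start low and late-start high share a cell at each visit before the first LTE infusion (Weeks 26, 50 and 78; Weeks 26 and 78 for PET) and have separate cells from Week 106 (Week 132 for PET). Keep the covariates, the covariance structure with its fallbacks, and the Kenward-Roger method. Keep the descriptive by-visit summaries by the four LTE groups.

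Add a sentence that the Week 26-78 dose-versus-placebo results of record are those of the placebo-controlled SAP. LTE-model estimates at those visits will still differ slightly even with the constraint, because the added LTE data affect the covariate and covariance estimates. If the constraint is not adopted, the minimum is to report LTE-model contrasts only at LTE visits and refer to the placebo-controlled analysis for the rest.

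The cost is SAP wording and a recoded class variable; no new data and no change in conduct. There are three downsides. The model tables show one placebo mean before the LTE, so the rule in 3.3.1 that efficacy is presented by four groups needs an exception. LTE estimates lean somewhat more on the fitted covariance. The constraint cannot carry into the single-visit ANCOVAs allowed for sparse visits.
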